#### In day 90, we will add the following question:

Over the last three months (you may choose more than one answer):

- 1. I started to take medications to improve my mental condition
- 2. I started psychological treatment

- 3. I contacted professionals (via email/phone/in person) regarding the possibly of starting a psychological treatment
- 4. I am planing to contact professionals regarding the possibility of starting a psychological treatment in the future
- 5. None of the above
- 6. Prefer not to answer

Please attach copies, unless standard instruments are used

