#### **Amendment**

Describe the change(s) being made

Currently, we assess participants at pre-intervention, post-intervention, 14-day follow-up and 30-day follow-up. For each step of the study the compensation fee is \$1.10.

We would like to add a 90-day follow-up, and conduct the same assessment as in 30-day follow-up and to add 1 item to inquire if the participant contacted mental health professionals.

In addition, the overall compensation for the study is now \$4.40.

Provide the rationale for the change(s)

We would like to understand longer-term effects of the intervention and if an observed change in help-seeking intentions is translate to change in help-seeking behavior.

Comment on the extent to which the proposed change(s) alter or affect risks/benefits to subjects We assess that there is no affect on risks/benefits to subject.

Comment on if the proposed change(s) require a modification to the Consent Form (CF)

We don't think a change in CF is needed.

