## **Study Procedures**

Describe the procedures required for this study

Participants will be randomly assigned to either a) a 120-second video-based intervention (day 1 and a "booster intervention" of the same content on day 14 of the study) featuring the personal story of a health care provider with COVID-19, his struggles and barriers to care, (b) video-based intervention (day 1 only), and a written description of the same story on day 14 (c) no-intervention control arm (questionnaires only).

Participants of all study arms will be invited to participate in a follow up survey in days 14, 30 and 90. We will invite the participants by using AMT messaging system.

The video content/written vignette: "Martha is a 35-year-old nurse who lives in NYC with her husband (Dave). She works at intensive care unit in a large hospital, and her husband was fired recently from his job as a waiter due to COVID-19. She has never been diagnosed with anxiety, depression or any other mental health issues. Lately, she finds herself experiencing nightmares as well as unexpected fears. She is feeling worried about money, about what might happen if she becomes infected with COVID-19, and about the safety of her parents as well. To Martha it seems that everything has changed since the pandemic began. Recently these worries mean she has had trouble falling asleep, she feels depressed and he feels anxious. Her husband suggested that she could try seeking help. When he first suggested this she dismissed him

saying, "What if people know I went to a psychologist? They might think I'm crazy. Also, what if they suggest I take meds? I don't want to take any... And if my colleges found out they might think I'm weak...". Martha was very resistant to even the idea at first. After a while however, when she realized that how she felt was only getting worse, she agreed to seek professional help. She found a therapist that she now meets with once a week, and since this started, she has reported that she is feeling much better."

You can upload charts or diagrams if any

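### The day-90 help-seeking item has no option for contact about medication, and its three-month look-back is not anchored to day 1

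*Combined protocol and SAP*

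**What the plan says.** The Amendment section asks "to add 1 item to inquire if the participant contacted mental health professionals". Its rationale is to learn "if an observed change in help-seeking intentions is translate to change in help-seeking behavior". Neither sentence limits the kind of care sought.

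The item itself is set out after Assessment Instruments. Its stem is "Over the last three months (you may choose more than one answer", and six tick boxes follow:

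- Option 1: "I started to take medications to improve my mental condition".
- Option 2: "I started psychological treatment".
- Option 3: "I contacted professionals (via email/phone/in person) regarding the possibly of starting a psychological treatment".
- Option 4: "I am planing to contact professionals regarding the possibility of starting a psychological treatment in the future".
- Options 5 and 6: none of the above, and a preference not to answer.

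On timing, Study Procedures says "Participants of all study arms will be invited to participate in a follow up survey in days 14, 30 and 90", through the AMT messaging system. Both video arms see the first video on day 1. No closing date or response window is given for any follow-up. The SAP models treatment-seeking intentions up to the 30-day follow-up. It gives no scoring rule or analysis for the day-90 item.

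**The concern.** Aim 1 and hypothesis 1 are about help-seeking behaviour. Among the instruments described, the other help-seeking measure is an attitude scale, and the COVID-19 behaviours questionnaire covers media use, social contact and testing. The day-90 item therefore carries the behavioural claim alone, and two features make it a weaker measure than it needs to be.

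First, the item is narrower than the purpose for which it was added. Medication counts only once it has been started, and contact counts only if it concerned psychological treatment. Contact about medication falls between the two. The plan itself treats medication as relevant: option 1 lists it, and the character in the video fears being offered it.

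Second, the look-back moves with the date of reply. Help sought soon after the video, when an effect might be expected, can fall outside the period that a late responder is asked about.

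If seekers are coded as non-seekers at the same rate in every arm, the difference between arms shrinks. The lost information cannot be rebuilt afterwards, because it was never collected.

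**Working it through.** The plan states no rate, power or scoring figure for this item, so there is nothing to reproduce.

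**1. Options against purpose**

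| What the participant did | Where the item puts them |
|---|---|
| Started medication | Option 1 |
| Started psychological treatment | Option 2 |
| Contacted a professional about psychological treatment, with or without medication | Option 3 |
| Contacted a professional solely about medication, not started | None of options 1-3. Option 4 only if also planning contact about psychological treatment, otherwise none of the above |
| Made no contact and has no plan | None of the above |

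The fourth row satisfies the Amendment's description (contact with a mental health professional) but normally gets the same code as the fifth.

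**2. Where the look-back opens**

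An answer on study day D comes D - 1 days after day 1. Three calendar months last L = 89 to 92 days. The window therefore opens (D - 1) - L days after day 1, and a negative value means before day 1.

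| Answered on day | Calculation | Window opens |
|---|---|---|
| 90 | 89 - (89 to 92) | 0 to 3 days before day 1 |
| 97 | 96 - (89 to 92) | 4 to 7 days after day 1 |
| 104 | 103 - (89 to 92) | 11 to 14 days after day 1 |
| 120 | 119 - (89 to 92) | 27 to 30 days after day 1 |

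A count over 365 possible start dates from 13 July 2020 gives the same ranges, with a mean of 2.3 days before day 1 for an answer on day 90. The reply days other than 90 are assumptions, since the documents give no distribution of lateness.

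**3. What missed seekers would do to a comparison (illustration)**

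Assumptions: true help-seeking of 10% in control and 16% in a video arm; 400 per arm (1,200 / 3, although no allocation ratio is stated); full response; and a fraction s of true seekers captured, equal in both arms. The two-sided 0.05 level is the SAP's.

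The observed rates are 0.10s and 0.16s, so the observed difference is 0.06s. Power is approximately Φ(difference / SE - 1.96), with SE = √{[p0(1 - p0) + p1(1 - p1)] / 400}.

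For s = 1, SE = √{(0.0900 + 0.1344) / 400} = 0.0237. Then 0.06 / 0.0237 = 2.53, and Φ(0.57) = 0.72.

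| s | Difference (points) | Power |
|---|---|---|
| 1.0 | 6.0 | 0.72 |
| 0.9 | 5.4 | 0.66 |
| 0.8 | 4.8 | 0.61 |
| 0.7 | 4.2 | 0.54 |

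With a pooled variance under the null, the powers are 0.71, 0.66, 0.60 and 0.54.

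**4. Why a scoring line is worth having**

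Suppose behaviour is equal, at 10% in both arms, and plan-only answers come from 10% of non-seekers in control and 20% in a video arm. An endpoint of any of options 1-4 would then have rates 0.10 + 0.90 × 0.10 = 0.19 and 0.10 + 0.90 × 0.20 = 0.28. With 400 per arm, that would be significant about 85% of the time with no difference in behaviour. The scoring here is hypothetical, because no document adopts it.

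**The case against.** The strongest reply on medication is that few people are lost. Anyone who started medication ticks option 1, and anyone who raised both kinds of care ticks option 3. Only those whose contact was solely about medication and led to no start within the window are missed. The intention scale also concerns professional psychological help, and the vignette ends with a weekly therapist, so option 3 matches the construct under study. It stands that the group may be small. It does not remove the mismatch, because the Amendment speaks of contact with mental health professionals in general and option 1 already counts medication.

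On the window, a reader might infer that the look-back does not start at the intervention. The documents do not support that: answered on day 90, it opens within about three days of day 1. Nor do they support a problem of early replies reaching well back before randomisation, since the invitation goes out at day 90 and no earlier access is described. Only late replies remain. Even then, a late responder is wrongly coded only if every relevant step fell in the dropped days.

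On option 4, a reader might infer that the item counts plans as behaviour. It does not. The option is a separate tick box, it refers to the future, and it can be set apart at analysis. Placing a plan under a past-tense stem is awkward wording. The gap is the missing scoring rule.

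**Conclusion.** The point holds in two parts. The contact option omits contact about medication, which is narrower than the Amendment's purpose and cannot be repaired at analysis. The look-back is also unanchored, with no response window: an answer on day 90 is unaffected, while answers on days 104 and 120 lose roughly the first 11-14 and 27-30 days after the video.

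The size of the resulting misclassification is unknown. The fall in power from 0.72 to between 0.66 and 0.54 rests wholly on assumed rates, assumed capture fractions, full response and 400 per arm. It also concerns a comparison that the SAP does not specify. A reader might take those figures as the size of the defect, but nothing in the documents ties a capture of 70-90% to participants whose contact was solely about medication.

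The correction is worth making because it is cheap and this item is the only measure of help-seeking behaviour described. The documents do not show that the item invalidates the day-90 wave.

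**What to change.** Make three changes, before the day-90 wave if possible:

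1. Widen option 3 to contact with a professional about starting psychological treatment or medication for mental health.
2. Replace the three-month stem with *Since you completed the first survey for this study*. No filled-in date is needed, so day-90 sessions need not be linked to day-1 records for this purpose.
3. Add one line to the SAP: help-seeking behaviour at day 90 is any of options 1-3 (yes/no), option 4 is reported separately as plans, and a preference not to answer is treated as missing.

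The cost is a minor amendment. If any day-90 answers have already been collected on the present wording, a sensitivity analysis is needed that separates the two wordings.

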### Research Related Delay to Treatment

Will research procedures result in a delay to treatment?

No

Treatment to be provided at the end of the study

None. No treatment is involved in this study, and the study does not prevent any participant from undergoing treatment for any medical problem.

#### Risks/Discomforts/Inconveniences

Risks that could be encountered during the study period

Breach of confidentiality is the main risk of the study. Another potential risk is that participants may experience mild psychological distress when answering questions about COVID-19, due to its sensitive nature.

Describe procedures for minimizing risks

For both of these risks, participants will be reminded that their responses are completely anonymous and that they are free to select "prefer not to answer" if they do not wish to answer a question or end their study participation at any time. Further ways to address the risk of breach of confidentiality are discussed in the Methods to Protect Confidentiality section.

## **Methods to Protect Confidentiality**

Describe methods to protect confidentiality

AMT protects confidentiality in keeping with the Amazon.com privacy policies. No identifiable information concerning participants' responses is shared with anyone outside the research team. The investigators of this research will only have access to the de-identified responses and associated demographic data of the respondents. We will not use any identifying information as IP addresses, and therefore will be unable to identify any individual respondent. Hence, we are requesting a waiver of the documentation of consent.

Will the study be conducted under a certificate of confidentiality?

No

### **Direct Benefits to Subjects**

Direct Benefits to Subjects
There is no foreseeable benefit to subjects.

# **Compensation and/or Reimbursement**

Will compensation or reimbursement for expenses be offered to subjects?

Please describe and indicate total amount and schedule of payment(s).

Include justification for compensation amounts and indicate if there are bonus payments.

Participants will be compensated \$4.40 in total for participating in the study (\$1.10 for day 1, \$1.10 for the follow-up on day 14, \$1.10 for the follow-up on day 30, and \$1.10 for the follow-up on day 90)), a competitive rate on AMT for such a short study. At the conclusion of each part of the study, a "completion code" is displayed to each participant by the Qualtrics software. Participants are instructed to input this code on the AMT web page where they signed up to participate in the study. Once a participant completes the study and inputs the correct code, the researchers will credit \$1.10 to his/her AMT user account on each day of participation (for a possible total of \$4.40). There are no bonus payments associated with this study.

### **Uploads**

Upload copy(ies) of unbolded Information Sheet(s)
Information Sheet. version 3. unbolded. 10.19.2020.pdf
Upload copy(ies) of bolded Information Sheet(s)
Information Sheet. version 3. bolded. 10.19.2020.pdf
Upload copy(ies) of recruitment materials/ads to be reviewed
Study Advertisement. version 3. unbolded. 10.19.2020.pdf
Study Advertisement. version 3. bolded. 10.19.2020.pdf
Upload copy(ies) of the HIPAA form
Upload any additional documents that may be related to this study
